3.0 Study Design

Phase 1 and Phase 2: Remote, randomized clinical trial using a 12-week, longitudinal SMART (Sequential Multiple Assignment Randomized Trial) design.

Phase 1, LEVEL 1 Randomization: Participants will be randomized to one of two conditions after completing baseline assessments: high monetary incentive and low monetary and feedback. After they are randomized to an incentive arm, they will then be randomized to either MBP or VBP. After six weeks of treatment, participants will move to level 2.

[figure not shown]
Phase 1, LEVEL 2 Randomization: Those who have made a 50% reduction to Patient Health Questionnaire-9 (PHQ-9)² scores to their assigned treatment will continue in that same treatment for 6 more weeks. Participants randomized to VBP who do not show 50% reduction in PHQ-9 scores will be randomized to either weekly VBP augmented with unlimited MBP (augmentation arm) or monthly VBP with unlimited MBP (switch arm).

Participants randomized to MBP who do not show a 50% reduction in PHQ-9 scores will be randomized to either unlimited MBP with weekly VBP (augmentation arm) or unlimited MBP and monthly VBP (minimal augmentation). The decision to switch or augment treatment after there is no response to treatment (described as a <50% change in PHQ-9 score) is based on treatment recommendations from the American Psychological Association, The

National Health Service in the UK, and the AHRQ depression guidelines. The Talkspace therapists, operating as consulting members of the study team, will complete the Clinical Global Impression – Improvement Scale after 5 weeks of treatment; if the participant does not complete a PHQ-9 in a timely manner for Level 2 randomization, this scale will be referenced for determining appropriateness for Level 2 randomization.

Phase 2, LEVEL 1 Randomization: Participants will be randomized to either MBP or weekly VBP. After six weeks of treatment, participants will move to Level 2.

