4.2 Participants

Phase 1: Estimated sample size of 200 participants.

Phase 2: Estimated sample size of 1,000 participants.

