4.3 Recruiting and Screening

Recruitment Sources: For both study phases, we will be recruiting from four primary sources, (1) traditional advertisements using newspaper, radio and podcast ads and stories, (2) social media sources such as Craigslist, Facebook, Twitter, and Instagram, (3) recruitment from people who are seeking care from Talkspace, and (4) advertisements on mental health sites such as Mental Health America. Potential participants will complete a screener survey hosted on REDCap.^{4,5} The study will also recruit from Prolific (starting late 2022) and ResearchMatch (starting early 2023).

Prolific Recruitment: For the Prolific recruitment survey, we will be using Prolific, an online recruitment tool for research. Users log in and complete research surveys and are paid an average of \$8.00 per hour for completing

surveys. The survey is confidential. Prolific users will self-identify by responding to the task. After a participant self-identifies as wanting to complete the task, they will be directed to an online REDCap survey. They will first review an information statement that contains all necessary elements of consent. After reviewing that text, if they decide to continue, they will complete a brief survey. Survey respondents who answer either "More than half the days" or "Nearly every day" to two or more of questions 5-8 will see information about the broader ADAPT study, including a link to the study. The information that will be shown is the same information included in recruitment materials previously approved by the IRB. We expect that responding to the survey will take up to 1 minute. After completion of the measures, each participant will be routed back to Prolific to certify completion of the survey. Payment for survey completion is handled by Prolific. If survey respondents choose to enroll in the ADAPT study, there will be no ability to link responses to the recruitment survey to any information gathered in the ADAPT study. All communication with survey respondents will take place within the Prolific platform.

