4.6 Study Enrollment Procedures

Consent Procedures:

Phase 1: The informed consent form will be completed via REDCap, with questions directed to the study team as needed. Participants will be told they will be randomized to one of two incentive levels as well as two levels of care. They will be told to use the treatment they are assigned as indicated (either weekly VBP appointments or unlimited MBP) for 6 weeks, and that they will complete daily and weekly surveys about their mood and functioning for 6 weeks. Participants will be told that 6 weeks after care, they will either continue with their treatment as assigned if they are seen to be responding or will be randomized to receive additional care if they are not responding to care. Finally, users will be told that participation at any point in the study is completely voluntary. After indicating they have read the consent, they will be asked questions about their understanding of the study. In order to continue on to the study, they must be able to answer the three comprehension questions correctly. We will be able to detect how users were recruited into the study by asking the participant how they learned about the study, including recommendations from friends or providers. Individuals who agree to participate will be identified in Talkspace's electronic health record as taking part in the study so that therapists can adhere to the study protocol.

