Phase 1: See Section 3.0. Randomization will be determined using www.randi2.org, an open-source web-based RCT randomizer that supports many types of algorithms (complete, biased coin, truncated randomization, block randomization, and the Wei's urn model randomization). Participants will be randomized to the first level of care using Wei's urn randomization blocking by recruitment, which adapts the probability of randomization to condition by the balance in the group assignments. This tightly controls balance while permitting randomization. Level 1 participants who respond to treatment will continue in their baseline condition. Level 1 participants who do not respond to treatment by week 5 (PHQ-9 score > 50% of baseline PHQ-9 score, or CGI-I score >2) will be re-randomized to receive MBP and supplemental weekly or monthly VBP.

Phase 2: See Section 3.0. Baseline Level 1 randomization to MBP or VBP occurred on REDCap and will be triggered by a research coordinator upon enrollment. We will use simple randomization with pre-specified and concealed blocks by therapist. Level 2 randomization will occur on REDCap. Level 1 participants who respond to treatment will continue in their baseline condition. Level 1 participants who do not respond to treatment by week 5 (PHQ-9 score > 50% of baseline PHQ-9 score, or CGI-I score >2) will be re-randomized to receive MBP and supplemental weekly or monthly VBP.

Treatment Procedures: All procedures described here are methods developed and used by Talkspace, unless otherwise specified. There are four interventions in this study: Level 1 interventions are unlimited MBP and weekly VBP. Level 2 interventions are MBP with monthly VBP, and MBP with weekly VBP. After participants give consent to participate, they will be randomized to one of the two Level 1 conditions. As per Talkspace's model, participants are offered a choice of three therapists, based on the state the therapist is licensed in. Procedures for consumer/clinician initiation are the same for each treatment option. Participants can contact their therapists any time after they are provided with choices. Once participants reach out to a therapist, therapists connect within 15 minutes to 24 hours, depending on the time of day the participants made their choice and the therapists' office

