8.0 Statistical Analysis Plan

Phase 1: We will compute descriptive statistics associated with confidence intervals that summarize recruitment rates, proportions completing instruments, attrition rates and time to drop out, missing data, and mean scale scores over time. Estimates of longitudinal change and condition-difference effect sizes will be computed. Comparisons will be conducted using pairwise methods, instead of omnibus ones, in order to highlight those groups that appear different. To determine the best incentive model for this study, we will calculate the proportion of the sample that completes daily, weekly and follow-up assessments. This will be benchmarked against what is considered acceptable retention in clinical trials, which is typically greater than 75% retention rates from baseline to final endpoint analysis, with an ideal of 80% retention. In preliminary study A3B (Baseline Mood Study), we were able to retain 80% of the sample providing 98% of all assessments with an incentive value of \$125 for a 12-week engagement. Should the low-incentive+feedback arm fall below this benchmark, we will use the incentive value of \$125 per participant in Phase 2. If we meet this target, we will use the incentive value of \$75 plus feedback per person in Phase 2. To determine overall drop-out rate, we will calculate the proportion who stop treatment but complete all assessments, and the proportion who drop from the study overall. Additionally, we will calculate whether there is a significant difference in drop-out rates among the two incentive arms and four treatment arms using Pearson's chi-square test. To calculate time to drop out, we will estimate and test a survival analysis model. The distribution of the 'survival' times for those assigned each incentive and treatment arm will be estimated, and nonparametric estimates of the survivor function will be computed by the Kaplan-Meier method. Curves will be tested using the log-rank and Tarone-Ware tests. Covariates, including baseline measures, will be included as covariates to test for their relationship to the survival function.

Phase 2: Phase 2 is a 12-week, randomized clinical trial using a sequential multiple assignment randomized trial (SMART) design (see protocol paper¹¹ and incentive paper¹²). Its goals are to:

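### Phase 1 balances MBP and VBP within recruitment groups, but the drop-out tests are not stratified by those groups: a small, avoidable loss of efficiency in that one comparison

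*Combined protocol and SAP*

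**What the plan says.** **Allocation.** Section 5.1 (Randomization, Phase 1) assigns the first level of care, MBP or VBP, by Wei's "urn randomization blocking by recruitment, which adapts the probability of randomization to condition by the balance in the group assignments". The term recruitment is not defined. I read it as recruitment source. Section 4.3 names four primary sources for both phases, and section 4.6 says of Phase 1: "We will be able to detect how users were recruited into the study by asking the participant how they learned about the study".

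The incentive draw is a separate, earlier step. Section 3.0 says: "After they are randomized to an incentive arm, they will then be randomized to either MBP or VBP". No method or blocking is given for that draw, or for the Level 2 re-randomization beyond who enters it.

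**Analysis.** Section 8.0 (Phase 1) says: "we will calculate whether there is a significant difference in drop-out rates among the two incentive arms and four treatment arms", using Pearson's chi-square. For time to drop-out it says: "Curves will be tested using the log-rank and Tarone-Ware tests". No stratum is named for any of these tests. Covariates, among them baseline measures, are also to enter the survival analysis, but recruitment group is not mentioned.

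**The concern.** When arms are balanced within groups that differ in drop-out, the allocation has already removed part of the between-group variation from the treatment contrast. An unstratified test still counts that variation as noise. Its standard error is then too large, its true size falls below the nominal level, and a real difference is a little easier to miss.

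Drop-out is a main outcome of Phase 1, and the sample is small. People already seeking Talkspace care could plausibly leave at a different rate from people reached by advertisements.

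The plan accepts the principle elsewhere. Phase 2 blocks by therapist, and section 8.0 then has the primary Phase 2 analyses account for provider, noting a possible gain in precision. Phase 1 has no matching sentence for recruitment group.

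**Working it through.** **Inputs from the documents**
- Phase 1 size: 200 (section 4.2).
- Recruitment groups: four primary sources (section 4.3).
- Allocation: urn within recruitment group, for the first level of care only (section 5.1).
- Overall drop-out: 100% − 80% = 20%, from the ideal retention in section 8.0.

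The plan gives no power, significance level or detectable difference for Phase 1, so there is no figure to reproduce.

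**Assumptions**
- The four sources are the urn's groups, each of 200/4 = 50.
- Tests are two-sided at 5%.
- Each draw adds one ball for the opposite arm. Starting the urn empty or with one ball per arm gave similar results.
- Drop-out rates by group are assumed throughout and varied over a range.

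**Step 1: analytic check**

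Let R² be the share of drop-out variance that lies between groups: R² = Var(group rates) / [p(1 − p)], where p is the mean rate. The urn balances only partly, removing about 2/3 of the chance imbalance. So:

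- SE inflation ≈ 1/√(1 − (2/3)R²)
- true size ≈ 2[1 − Φ(1.96 × inflation)]

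Rates 5/10/25/40%: the mean is 20% and the deviations are −15, −10, +5 and +20 points. The variance is (225 + 100 + 25 + 400)/4 = 187.5 squared points = 0.01875. R² = 0.01875/0.16 = 0.117, inflation = 1.042, and size = 4.1%.

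Rates 5/15/35/55%: the mean is 27.5% and the variance is 0.036875. R² = 0.036875/0.199375 = 0.185, inflation = 1.068, and size = 3.6%.

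**Step 2: simulation of MBP versus VBP**

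The Pearson test is compared with a Cochran-Mantel-Haenszel (CMH) test stratified by group. Rows at odds ratio 2.4 use 40,000 runs and an empty starting urn. The others use 8,000 runs and a start of one ball per arm. Size is the rejection rate at odds ratio 1.

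| Assumed drop-out by group | Size, Pearson / CMH | Odds ratio | Power, Pearson / CMH | CMH gain (points) |
|---|---|---|---|---|
| 20% in all | 5.2% / 5.2% | 2.4 | 69.5% / 69.0% | −0.5 |
| 15/18/22/25% | 4.9% / 4.8% | 2.4 | 68.5% / 68.5% | 0 |
| 10/15/25/30% | 4.8% / 5.0% | 2.4 | 66.3% / 67.4% | 1.1 |
| 10/20/30/40% | 4.9% / 5.1% | 2.0 | 55.6% / 58.4% | 2.8 |
| same | same | 2.5 | 80.2% / 82.4% | 2.2 |
| 5/10/25/40% | 4.2% / 4.9% | 2.4 | 58.5% / 63.2% | 4.7 |
| 5/5/35/35% | 4.1% / 5.0% | 2.4 | 56.1% / 61.9% | 5.8 |
| 5/15/35/55% | 3.6% / 5.2% | 2.0 | 43.7% / 52.1% | 8.4 |
| same | same | 2.5 | 68.1% / 76.5% | 8.4 |

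The simulated sizes agree with Step 1.

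**Step 3: the same settings without blocking**

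Under simple randomization, one possibility for the incentive draw, Pearson size stays at 5.0% to 5.1% in all five settings run at odds ratio 2.4. The CMH test still gains power: 58.2% to 62.6% at 5/10/25/40%. So the loss of size comes from the urn, while the power gain is what adjusting for a predictive factor gives under either scheme.

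**Step 4: scale**

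With 100 per arm, power is 37% for 20% versus 30% drop-out and reaches 80% only at about 20% versus 38%. Sample size limits these tests far more than the missing strata.

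The log-rank and Tarone-Ware tests were not simulated. The same reasoning gives the direction for them, not a figure.

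**The case against.** The strongest reply is that recruitment group may hardly have varied. Section 4.4 says that before early 2023 all recruitment so far had come through advertisements on mental health platforms. Phase 1 appears to have ended by then: section 4.5 sets Phase 2 payments from what Phase 1 taught, and section 8.0 cites an incentive paper that the reference list dates to 2022. If there was in effect one channel, there is nothing to gain. This largely stands, though it is not conclusive: the sentence sits in a Phase 2 paragraph, and section 4.3 lists four sources for both phases.

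Second, the rates by group are assumed. The largest figure needs an 11-fold spread (5% to 55%); around 20% overall the gain is 0 to about 6 points. This stands and is why the size is given as a range.

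Third, the chi-square in section 8.0 is worded for two incentive arms and four treatment arms. Two of the four interventions in section 5.1 are reached only by re-randomizing non-responders. This also stands: the urn bears only on the Level 1 contrast.

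Fourth, the covariates in the survival analysis might include recruitment group. They might, but that would not alter the chi-square or the curve tests as named.

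None of this reverses the direction, and where group does not matter, stratifying costs about half a point of power.

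**Conclusion.** The point holds as a minor matter of efficiency in the Phase 1 MBP versus VBP drop-out comparison. If drop-out differs by recruitment group, the unstratified Pearson test has true size of about 3.6% to 5%. The power given up runs from none, through 1 to 3 points at a moderate spread, to about 8 points at an extreme one. This rests on reading recruitment as source, on four equal groups, and on the assumed rates.

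Three stronger readings are not supported:
- **That every Phase 1 drop-out test has error bars that are too wide.** Blocking is stated only for the first level of care. The incentive test is not shown to be mis-sized, nor are comparisons of the re-randomized arms.
- **That the incentive choice is at risk.** Section 8.0 settles it by a retention benchmark in the low-incentive arm, not by a between-arm test.
- **That the tests are invalid.** The error is on the conservative side.

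**What to change.** 1. In section 5.1, define the recruitment groups used by the urn.
2. In section 8.0, for the Level 1 MBP versus VBP drop-out comparison, use a Cochran-Mantel-Haenszel test and stratified log-rank and Tarone-Ware tests with those groups as strata. Merge very small groups by a rule set without reference to drop-out by arm. Report the stratified risk difference with its interval.
3. State whether recruitment group is among the covariates of the survival analysis.
4. The same strata may be used for the incentive comparison as an optional gain in precision. It should not be presented as a correction.

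If Phase 1 has already been analysed, report the stratified results beside the planned tests and label them supplementary. The cost is a few sentences and a short re-run on data that section 4.6 says are collected. If only one channel was in use, a statement to that effect is enough.

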Phase 2, LEVEL 2 Randomization: Those who have made a 50% reduction to PHQ-9 scores to their assigned treatment will continue in that same treatment for 6 more weeks. Participants randomized to VBP who do not show 50% reduction in PHQ-9 scores will be randomized to either weekly VBP augmented with unlimited MBP (augmentation arm) or monthly VBP with unlimited MBP (switch arm). Participants randomized to MBP who do not show a 50% reduction in PHQ-9 scores will be randomized to either unlimited MBP with weekly VBP (augmentation arm) or unlimited MBP and monthly VBP (minimal augmentation). The decision to switch or augment treatment after there is no response to treatment (<50% change in PHQ-9 score) is based on treatment recommendations from the American Psychological Association, The National Health Service in the UK, and the AHRQ depression guidelines. Talkspace therapists, operating as consulting members of the study team, will complete the Clinical Global Impression – Improvement Scale³ after 5 weeks of treatment; if the participant does not complete a PHQ-9 in any one of the weekly assessments at weeks 3, 4, or 5 in the study timeline, this scale will be referenced for determining appropriateness for Level 2 randomization.

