1. Test effectiveness of unlimited daily, message-based psychotherapy (MBP) for depression, compared to weekly traditionally delivered, videoconferencing-based psychotherapy (VBP). Level 1 conditions: unlimited MBP and weekly VBP.
2. Develop an evidence-based treatment sequence for those who do not respond to either MBP or VBP. Level 2 conditions for participants who do not respond to treatment: MBP+VBP_{weekly} (switch from MBP to weekly VBP with MBP), MBP+VBP_{monthly} (switch from MBP to monthly VBP with MBP), VBP_{weekly}+MBP (switch from VBP to weekly VBP with MBP), and VBP_{monthly}+MBP (switch from VBP to monthly VBP with MBP).

Hypothesis 1: Compared to those randomized to weekly video care at baseline, patients randomized to message-based care will have greater improvements in depression (1a) and social functioning (1b), be more likely to show a treatment response (1c), and be more likely to experience remission (1d) at 5 and 12 weeks of care. Hypothesis 2: For those who fail to respond to treatment from baseline to 5 weeks, those re-randomized to receive (or retain) weekly video care will have greater improvements in depression and be more likely to show a response to treatment than those randomized to monthly video care. Hypothesis 3 (moderator): Baseline anxiety will moderate improvement in depression such that those with greater anxiety will have better response to message-based care at 5 and 12 weeks than to video-based care. Exploratory Aims: Exploratory evaluation of differences among groups in treatment engagement by week 5, ratings of therapeutic alliance at weeks 4 and 10, ratings of

quality of care and amount helped by treatment at week 10, and ratings of goal satisfaction, plans to continue using treatment, and likelihood to recommend treatment to others at week 12.

Sample Size and Power: We propose to screen 4,789 potential participants, anticipating we will enroll 1,250 participants to arrive at a final sample of 1,000 evaluated participants, assuming a 20% dropout rate by the last assessment. In our previous psychotherapy studies, dropout rates have been on the order of 10% by final assessment. In our recent on-line studies with Google Verily, drop out has been on the order of 20%. Our large incentive arm, tested in Phase 1, is based on the incentive analyses done on the Baseline Mood Study at Verily.

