Level 1 Power: For the quantitative primary outcome (PHQ-9) we have greater than 80% power to detect a 0.20 standard deviation across groups which corresponds to a clinically meaningful small difference. For a binary success indicator, we will consider a 50% reduction in PHQ-9 from baseline to week 5, and we have greater than 80% power to detect an absolute difference of 10% (e.g., 60% of subjects with >50% improvement versus 70% of subjects with >50% improvement).

Level 2 Power: The primary comparison in the second stage is the comparison of the Ultimate Plan (UP; MBP with weekly VBP) versus the Premium Plan (PP; MBP with monthly VBP) for each of the first stage randomization groups (MBP and VBP). We expect a second stage analysis sample of 324 subjects, and this corresponds to 80% power to detect a 0.32 standard deviation difference across the UP and PP groups when pooling across the primary MBP and VBP strata. Our primary second stage analysis will construct an overall UP versus PP difference stratifying on first stage randomization, and secondary analysis will consider the UP versus PP difference within the MBP and VBP groups separately.

Accounting for Provider Effects: Each provider will treat both MBP and VBP patients. Therefore, our primary analyses will all cluster on provider either using linear mixed models or generalized estimating equations to yield valid statistical inference. However, since treatment condition will vary within provider, the impact of provider clustering is to effectively balance or control for provider effects. Therefore, our power calculations are conservative since they do not account for the potential increase in precision associated with control for provider effects. Such within-provider randomization is in contrast to traditional cluster randomized trials where providers treat all patients in one study condition and thus increase variability associated with treatment comparisons through the well-known intra-cluster correlation coefficient.

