Hypothesis	Timepoint(s)	Statistical Test	Contrast/analysis of interest
1a: Compared to those randomized to weekly video care at baseline, patients randomized to message-based care will have greater improvements in depression	Baseline to W5	3-level mixed effects model	MBP vs VBP
1b: Compared to those randomized to weekly video care at baseline, patients randomized to message-based care will have greater improvements in social functioning	Baseline to W12	3-level mixed effects model	MBP vs VBP
1c: Compared to those randomized to weekly video care at baseline, patients randomized to message-based care will be more likely to show a treatment response at 5 and 12 weeks of care.	Between W3 to W5 / W12	Chi-square tests	MBP vs VBP
1d: Compared to those randomized to weekly video care at baseline, patients randomized to message-based care will be more likely to experience remission at 5 and 12 weeks of care.	Between W3 to W5 / W12	Chi-square tests	MBP vs VBP
2: For those who fail to respond to treatment from baseline to 5 weeks, those re-randomized to receive (or retain) weekly video care will have greater improvements in depression than those randomized to monthly video care	W6 to W12	3-level mixed effects model with time centered at week 6	MBP+VBP _{weekly} vs MBP+VBP _{monthly} ; VBP _{weekly} +MBP vs VBP _{monthly} +MBP
2: For those who fail to respond to treatment from baseline to 5 weeks, those re-randomized to receive (or retain) weekly video care will be more likely to show a response to treatment than those randomized to monthly video care	W12	Chi-square test	MBP+VBP _{weekly} vs MBP+VBP _{monthly} ; VBP _{weekly} +MBP vs VBP _{monthly} +MBP
3 (moderator): Baseline anxiety will moderate improvement in depression such that those with greater anxiety will have better response to message-based care at 5 and 12 weeks than to video-based care.	Baseline to W12	3-level mixed effects model, with mean-centered baseline GAD-7	MBP vs VBP

Exploratory: We will explore whether there will be differences among groups in treatment engagement by week 5	Between W3 to W5	Chi-square test	MBP vs VBP
Exploratory: We will explore whether there will be differences among groups in ratings of therapeutic alliance	W4 / W10	2-level mixed effects models	W4: Level 1 conditions (MBP vs VBP); W10: Level 2 conditions (MBP vs VBP; MBP+VBP _{monthly} vs MBP+VBP _{weekly} ; VBP _{monthly} +MBP vs VBP _{monthly} +MBP)

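### Section 5.1 restates the Level 2 re-randomization rule without Section 3.0's condition that CGI-I is used when the PHQ-9 was not completed

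*Combined protocol and SAP*

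**What the plan says.** Section 3.0 (Study Design) makes the PHQ-9 the deciding measure. For Phase 2 it says: "Those who have made a 50% reduction to PHQ-9 scores to their assigned treatment will continue in that same treatment". Participants below that threshold are re-randomized. Therapists complete the CGI-I after 5 weeks of treatment, and 3.0 gives it a fallback role. In Phase 1 it is referenced "if the participant does not complete a PHQ-9 in a timely manner for Level 2 randomization"; in Phase 2, "if the participant does not complete a PHQ-9 in any one of the weekly assessments at weeks 3, 4, or 5". Section 3.0 gives no CGI-I cut-off.

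Section 5.1 (Procedures, Randomization) restates the rule in the same words for both phases. Non-response by week 5 is "PHQ-9 score > 50% of baseline PHQ-9 score, or CGI-I score >2". The sentence carries no missing-PHQ-9 condition, but each of the two paragraphs opens by pointing to Section 3.0.

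Section 8.0 describes week-5 success by PHQ-9 alone (Level 1 Power): "we will consider a 50% reduction in PHQ-9 from baseline to week 5". Hypothesis 2 is framed as "For those who fail to respond to treatment from baseline to 5 weeks".

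**The concern.** In a SMART, the response rule assigns treatment. It decides who stays on the Level 1 treatment, who is re-randomized, and who makes up the Hypothesis 2 population. Section 5.1 joins its two criteria with an unconditional *or*, so a poor CGI-I rating alone would trigger re-randomization even when a PHQ-9 shows response.

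The case can arise. Section 3.0 has therapists complete the CGI-I after 5 weeks without limiting this to participants who lack a PHQ-9, so both scores would often exist together. Section 5.1 is also the only place that gives the CGI-I cut-off, so anyone setting up the rule has to take it from the sentence that lacks the condition.

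If the literal rule were run, some PHQ-9 responders would change treatment at week 6 and be analysed as non-responders. One Hypothesis 2 test in Table 2 is that the weekly group "will be more likely to show a response to treatment than those randomized to monthly video care" at W12. If response at W12 means the same 50% reduction from baseline (an assumption, since Section 8.0 spells it out only for week 5), these people would already meet that criterion on entering Level 2.

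**Working it through.** The check is mainly a comparison of texts. There is no stated figure to reproduce.

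**Step 1: do the PHQ-9 parts agree?** Let *b* be the baseline score and *w* the later score. Section 5.1 calls non-response *w* > 0.5*b*. Section 3.0 calls it a change below 50%, that is (*b* − *w*)/*b* < 0.5. Rearranging the second gives *w* > 0.5*b*, so they are identical. Enumerating baselines 5 to 27 against later scores 0 to 27 (23 × 28 = 644 pairs) finds 0 mismatches. Any disagreement must therefore come from the CGI-I clause.

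**Step 2: apply both texts to one example.** Take a baseline PHQ-9 of 16, so the cut-off is 0.5 × 16 = 8. A score of 7 is 7/16 = 43.75% of baseline, a 56.25% reduction (response). A score of 10 is 10/16 = 62.5% of baseline, a 37.5% reduction (non-response).

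| PHQ-9 | CGI-I | Section 3.0 | Section 5.1, literal |
|---|---|---|---|
| 7 | 2 | continue | continue |
| 7 | 3 | continue | **re-randomize** |
| 10 | 2 | re-randomize | re-randomize |
| 10 | 3 | re-randomize | re-randomize |
| missing | 2 | continue* | continue |
| missing | 3 | re-randomize* | re-randomize |

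*Section 3.0 has no CGI-I cut-off, so these two entries borrow the one in 5.1.

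With a PHQ-9 available, the texts agree in three of four combinations and differ in one: PHQ-9 at or below 50% of baseline with CGI-I above 2.

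**Step 3: how firm is that boundary?** The table reads the Phase 2 fallback as applying when no PHQ-9 was completed at weeks 3, 4 or 5. The phrase "if the participant does not complete a PHQ-9 in any one of the weekly assessments at weeks 3, 4, or 5" can also be read as applying when any one of the three was missed. On that reading, CGI-I could be consulted for people who do have a PHQ-9 from another of those weeks, and 3.0 itself would not be strictly PHQ-9-first. The single conflicting cell therefore rests on the first reading, which seems the more natural one.

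**Step 4: what follows for the analyses?**
- Hypothesis 2: the weekly and monthly groups are still formed by randomization, so their contrast is not biased. Its population would include people who are not non-responders by PHQ-9.
- Comparisons of MBP with VBP up to week 5 precede Level 2 and are unaffected.
- Size: the documents give no distribution of CGI-I scores and no rate of disagreement with the PHQ-9. Neither the number affected nor any change in power can be derived.

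**The case against.** The strongest reply is that there is only one rule, spread over two sections. Both paragraphs in 5.1 refer to 3.0; 3.0 supplies the order (PHQ-9 first, CGI-I if it is missing) and 5.1 supplies the missing cut-off. Neither section works without the other. The context supports this: 5.1 also says that responders stay in their baseline condition, 3.0 defines non-response by PHQ-9 change, Section 8.0 does the same for week-5 success, and nowhere is CGI-I said to override an available PHQ-9. The table above itself needs the 5.1 cut-off to complete 3.0.

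Most of this stands. A reader might infer that the plan contains two rival re-randomization rules; the cross-reference makes an incomplete restatement more likely. Strictly, 3.0 says that CGI-I will be referenced if the PHQ-9 is lacking. That this is the only circumstance is implied, not stated.

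The reply does not remove the point. The cross-reference opens a whole paragraph on randomization and is not tied to the CGI-I clause. In Phase 2 the sentence closely follows the statement that Level 2 randomization takes place on REDCap, so it reads as the operating instruction. The section it defers to has an ambiguous fallback phrase of its own.

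It is also fair to say that the documents do not name which PHQ-9 counts when several exist; Table 2 gives the window for response only as "Between W3 to W5 / W12". That is missing detail, a separate matter, and adds no weight here.

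**Conclusion.** The point holds as a minor error of wording in a treatment-assignment rule. Followed literally, 5.1 assigns a PHQ-9 responder with CGI-I above 2 differently from 3.0 and changes the population of Hypothesis 2. High confidence applies to the omitted condition; it does not extend to any claim that the trial used the literal rule, on which the documents are silent.

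Two stronger conclusions are tempting and unsupported. One is that Hypothesis 2 is biased: its contrast stays randomized, and the issue is whom the result describes. The other is that the expected second-stage sample of 324 or its stated power is wrong: without CGI-I rates, no effect on either can be worked out.

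The verdict assumes that the Phase 2 fallback means no PHQ-9 at any of the three weeks. The remark about the W12 response test further assumes the same 50% definition there. If 5.1 is simply shorthand for 3.0 and was run that way, nothing in the results is affected.

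**What to change.** In Section 5.1, for both phases, make the second criterion conditional: *PHQ-9 score > 50% of baseline or, only if no PHQ-9 is available as defined in Section 3.0, CGI-I score >2*. Deferring to 3.0 keeps the different Phase 1 and Phase 2 conditions in one place.

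In Section 3.0, Phase 2, reword the fallback as *does not complete a PHQ-9 at any of weeks 3, 4 or 5*.

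The cost is one clause in each 5.1 paragraph and one phrase in 3.0, with no new data. Only if the literal *or* was already run in REDCap, say so and report Hypothesis 2 with and without the PHQ-9 responders who were re-randomized on CGI-I.
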